6. DATA ANALYSIS AND MANAGEMENT*

Statistical Procedures and Power Analysis.

Study design will allow systematic quantification (mean and variance) of the effects of NEATCap device and SVS mattress on automatic function, such as breathing (IBI), cardiac rhythm (R-R), frequency and duration of body movements (e.g., defined via streamlined video, artifact in pulse-oximeter plethysmographic activity, and actigraph count), blood oxygenation (e.g., durations<85%), skin temperature, and sleep states. Analyses will be conducted to determine whether interventions impinge on neural oscillators that drive breathing and cardiac control, and whether NEATCap device reduces dangerous levels of environmental noise, to improve autonomic function and sleep activity.

NCT03881553 Study Protocol and Statistical Analysis Plan

Signal processing algorithms will be used to characterize separately the instability of physiological signals, such as respiration and heartbeat. We will explore, for example, whether different durations of movement periods (e.g., 1.5-5 sec; >5 sec; >10sec) have unique relationships with withdrawal (NAS or iatrogenic) or prematurity, and are affected differently with different interventions (NEATCap device and SVS Mattress).

Parametric tests will be used for analyses of all continuous variables. The Friedman's and Wilcoxon signed-rank tests will be used for nonparametric analyses. For analyses of parametric data separate repeated measures ANOVAs will test effects of stimulus condition (ON or OFF) and trial order. Post-hoc pairwise t-tests will determine differences in responses for conditions of stimulation ON and OFF. For example, separate repeated measures ANOVAs will test effects of stimulus condition (ON or OFF) and trial order on physiological variables. Time of intervention (e.g., infant age, severity of NAS) will be a covariate to assess whether there are critical periods in infant development for optimizing the intervention as a therapeutic strategy. Pearson product-moment correlation coefficient analysis will be used to establish associations between breathing stability (IBI variance) and movement duration, with the expectation that greater variance in respiratory parameters will be positively correlated with excessive movement. *P* values of <0.05 will be considered significant.

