The number of periods and duration of intervention will not always be the same for each study session. The proposed study will test if different modes (NEATCap; Mattress SVS) affects duration of the interfeed interval, improves autonomic function, and promotes sleep. This is a within-subjects design, so all subjects will receive intervals of routine clinical care in addition to the assigned intervention/s complementary to routine care. Intervention assignment for study session is based on equipment availability, research personnel availability; it will not be determined by the subject's treating physician.

- It is possible that a subject does not receive an intervention (participate in a study session) after enrollment if: 1) We have technical difficulties and are unable to conduct studies; 2) Subject is discharged before being entered into an intervention stimulation session; 3) Doctor treating child requests we terminate the study – we will heed to the discretion of the Attending Physician or primary medical caregiver for decisions regarding termination of an infant from the study for example due to sickness, sepsis or exacerbated withdrawal symptoms (e.g., seizures) – such population of subjects will likely already be excluded by the exclusion criteria, but others unknown at this time may also ensue. Medical criteria for terminating a subject from the study will be determined by the medical caregiver treating the infant. Authorized parent, nurse or investigator may stop/postpone a study session for reasons such as excessive symptomatology preventing ability to properly study the subject (e.g., unable to keep sensors in place, infant needs to be held incessantly, skin rash), parent has visitors or simply doesn't want an infant/child studied on a particular day – this would not result in termination from the study per se. If we find that a mode of stimulation appears to make the infant/child irritable (e.g., excessive waking, crying, movement), we will end the study session for that day. If this happens on a second study-session day, we will discontinue study.

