7. PROVISIONS TO MONITOR THE DATA TO ENSURE THE SAFETY OF SUBJECTS*

NCT03881553 Study Protocol and Statistical Analysis Plan

An independent medical safety monitor will review serious adverse events reported to the IRB and will summarize each in a written report that will be submitted to the Center for Advancing Point of Care Technologies (CAPCaT) for any required reporting to NIH.

This research does not involve more than minimal risk to subjects. While it may be difficult to determine whether NEATCap or SVS mattress causes worsening of physiological function or is related to common system dysregulation of the subject, a study may be discontinued at any time if the investigators or the subject's medical caregiver suspects there are any adverse effects on breathing, heart rate, thermoregulation, oxygenation, movement or any other function.

Nurses are instructed to provide routine care and to intervene as they would typically do, e.g., in the event of a prolonged apnea, bradycardia or blood-oxygen desaturation, despite the presence of an investigator by the subject's bedside. The protocol may be ended if intervention is associated with noticeable exacerbation of irritability including disproportionate awakening, cardio-respiratory instabilities, and/or excessive rise in temperature as observed by a medical caregiver, researcher, or parent at bedside during a study session. Parent/Guardian or medical staff may terminate the study (subject withdrawn) or request not to part-take in any procedure/s at any time (subject remains in study). Our studies are conducted at the bedside so we are in frequent contact with the clinical staff; we will routinely seek informal feedback from the medical-care staff to ensure the safety of our study protocols. The medical-care staff and parent/guardian are encouraged to call us if they have any specific concerns throughout the study enrollment.

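### Sessions are ended for apparent bad responses to the device, in outcomes that are then compared ON with OFF, and section 6 has no rule for analysing them; either simple reading of the planned test is biased

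*Combined protocol and SAP*

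**What the plan says.** **Outcomes.** Section 6 compares breathing, cardiac rhythm, the frequency and duration of body movements, and "blood oxygenation (e.g., durations<85%), skin temperature, and sleep states". The stated aim is to test whether each device "affects duration of the interfeed interval, improves autonomic function, and promotes sleep".

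**Test.** "For analyses of parametric data separate repeated measures ANOVAs will test effects of stimulus condition (ON or OFF) and trial order". This is followed by "Post-hoc pairwise t-tests will determine differences in responses for conditions of stimulation ON and OFF". Friedman and Wilcoxon signed-rank tests are listed for nonparametric analyses.

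**Mandatory stop.** Later in section 6, if a mode of stimulation "appears to make the infant/child irritable (e.g., excessive waking, crying, movement), we will end the study session for that day". Then: "If this happens on a second study-session day, we will discontinue study".

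**Discretionary stop.** Section 7: "The protocol may be ended if intervention is associated with noticeable exacerbation of irritability including disproportionate awakening, cardio-respiratory instabilities", and the sentence goes on to excessive temperature rise.

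**Uneven data.** Section 6 accepts that "The number of periods and duration of intervention will not always be the same for each study session". No section gives a missing-data rule, an analysis set, or a rule for a period cut short.

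**The concern.** A session is ended because of how the child seems to respond to the device, and apart from crying the triggers are among the outcomes analysed. The data that go missing are therefore selected on the ON response.

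The named test does not deal with this. With condition and trial order as within-child factors, a standard repeated measures ANOVA needs a value in every condition-by-order cell. A child stopped in an early ON period lacks the later cells and would drop out by default. Friedman's test likewise needs complete blocks. The pairwise t-tests and the Wilcoxon test need only one ON and one OFF value per child. They could keep that child, but with an ON mean that stops at its worst point.

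At stake are a false claim that a device calms movement or improves sleep, a false claim that it does the reverse, and the loss of a real harm from the ON/OFF comparison.

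**Working it through.** The documents give no power figure to reproduce, and no sample size, variance or stop rate. Everything below except the design features is assumed and shown as a range.

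**1. Inputs.** From the documents: alternating OFF and ON periods of about 3-4 hours, sessions of about 8-12 hours (section 4), and P < 0.05 (section 6; two-sided assumed). Assumed:
- 50 children, one OFF-ON-OFF-ON session each, six 30-minute epochs per period.
- Epoch SD 1, period SD 0.3, child SD 1. SD of the child's own ON response 0, 0.3, 0.5 or 0.8, with mean effect 0.
- Higher values are worse. A session stops in ON when the mean of the last hour exceeds the preceding OFF mean by a cut-off chosen so that 5%, 10% or 20% of children stop.

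**2. Test statistic.** Per child, D = (ON1 + ON2)/2 - (OFF1 + OFF2)/2. The condition effect of the complete-cell ANOVA is the paired test t = mean(D)/(SD(D)/√n). A period mean has variance 0.3² + 1²/6 = 0.257. So Var(D) = 0.257 + (SD of ON response)², and SD(D) runs from 0.51 to 0.95. With no stopping, each one-sided error rate is 2.3-2.7%, as it should be.

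**3. Who has an empty cell.** In this layout 39-50% of stops fall in the second, final ON period. Those children have a value in all four cells, the last one shortened. Only the other 50-61% of stopped children have empty cells.

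**4. Results, no true effect, n = 50, nominal 2.5%.**

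| Handling | Error | 5% stopped | 10% | 20% |
|---|---|---|---|---|
| Drop children with an empty cell | 'better' | 4-6% | 6-10% | 9-24% |
| Drop every stopped child | 'better' | 8-10% | 16-24% | 41-68% |
| Available-period means, full weight | 'worse' | 3-5% | 4-7% | 7-19% |
| Mixed model, all epochs to the stop | 'better' | 1.5-3.3% over all rates | | |
| Mixed model, all epochs to the stop | 'worse' | 1.9-2.9% over all rates | | |

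These are simulated rates. The ends of the ranges move by one to three percentage points between runs.

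Bias in SDs of D is -0.03 to -0.05, -0.05 to -0.09 and -0.09 to -0.18 for the first row, and -0.08 to -0.10, -0.14 to -0.17 and -0.25 to -0.32 for the second. For the mixed model it is within 0.01.

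**5. Hand check of the first row.** The rate is roughly Φ(-1.96 + |bias| × √n kept). At 10% stopped about 47 children remain (√47 = 6.86). Bias 0.05 gives Φ(-1.62) = 5.3%, and 0.09 gives Φ(-1.34) = 9.0%. At 20% stopped about 45 remain (√45 = 6.71). Bias 0.09 gives Φ(-1.36) = 8.7%, and 0.18 gives Φ(-0.75) = 22.7%. Both agree with the table.

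**6. A different set-up.** Here n = 40, there is one value per period with residual SD 1, the SD of the ON response is 0.5, and the bedside decision carries noise. Stops come only after the first ON period, so every stopped child has empty cells. At 5%, 10% and 20% stopped:
- Complete cells: bias -0.09, -0.15 and -0.27; false 'better' 6.0%, 13.3% and 31.6%.
- Available-period means: bias +0.06, +0.12 and +0.18; false 'worse' 3.4%, 6.7% and 13.1%.
- Mixed model: no material bias.

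With a true harm of +0.30 and the same cut-offs (7%, 14% and 26% then stop), complete cells estimate +0.19, +0.10 and -0.04. Available-period means give +0.39, +0.44 and +0.51, and the mixed model 0.30-0.31.

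**7. Low stop rates.** Section 4 reports use of the SVS mattress in over 100 premature and over 50 opioid-exposed infants with no incident or evident side effect. If that meant 0 ended sessions in 150 infants (an assumption), the one-sided 95% upper limit is 1 - 0.05^(1/150) = 2.0%. At 1-2% stopped, false 'better' is 2.6-3.2% when empty-cell children are dropped and 3.1-4.6% when all stopped children are.

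**The case against.** A reader might infer that the plan removes the worst responders and so favours the device. The documents do not say so. Exclusion follows only from the standard form of the ANOVA. Section 6 accepts unequal numbers of periods, so a strict complete-cell layout would also lose children for unrelated reasons, and reduction to condition means is at least as plausible. That would reverse the sign of the bias. The direction is therefore open.

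A reader might also infer that only ON is ever cut short. Section 6 lets a parent, nurse or investigator stop or postpone a session when symptoms are too severe to study the child properly, whatever the condition. Such stops can fall in OFF and are not modelled above. They do not cancel a rule tied to apparent stimulation effects, but they weaken any claim of pure one-sidedness.

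Nor is a stopped child lost at once. A first stop ends only that day, and up to four sessions are allowed. The section 7 trigger, including temperature, is discretionary, so it cannot be read as a rule that warming ends a session.

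The size is also uncertain. The mattress experience points to few stops, though it is not a count of ended sessions and does not cover NEATCap. Bedside judgement may follow the recorded outcome only loosely: at a correlation of 0.5, dropping every stopped child (n = 50) gives 4-6%, 7-9% and 14-17%.

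All of this stands as a limit on direction and size. It does not supply the missing rule.

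**Conclusion.** The concern holds in conditional form. The mandatory irritability rule alone makes missing ON data depend on outcomes that are analysed, and the plan names a test without saying how ended sessions enter it. Complete cells bias the result towards the device, and available-period means at full weight bias it against.

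The inflation is modest if only children with an empty cell are lost, large if every stopped child is dropped and 10% or more stop, and small at 2% or fewer. These sizes rest on the assumed sample size, variances, session layout and stopping threshold. What does not depend on the exact figures is that both simple routes are biased and that a mixed model on recorded data avoids this when stopping depends on recorded responses. A demonstrated bias in favour of the device is not supported. This should be changed, with medium confidence.

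**What to change.** In section 6, replace the repeated measures ANOVA with a mixed model on all data recorded up to the stop.
- **Data:** epochs (for example 30 minutes) for continuous signals; one value per interval for interfeed interval, which epochs do not suit.
- **Model:** fixed effects for condition and trial order; random effects for child, child-by-condition and period.
- **Analysis set:** state that no child or session is excluded because it was ended.
- **Reporting:** number of ended sessions by device, condition in force and reason.
- **Sensitivity analysis:** the Wilcoxon signed-rank test already listed, with a session ended in ON ranked as the worst ON response.

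The cost is SAP wording, the work of cutting recordings into epochs, and one log field for stop time and reason. Section 4 already provides for recording throughout the session and logging of condition timing. The model is valid only if stopping depends on recorded responses; if staff stop for something unrecorded, some bias remains. The sensitivity analysis covers that case but leans against the device, so it should not replace the main analysis.

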Study Sessions. The study will be conducted in the UMass Memorial NICU/CCN and in the UMass Memorial Children's Medical Center PICU/PIU. The subject will be studied in the unit in which he/she is receiving care. Enrollment in this study allows the subject to participate in up to 4 full-recording study sessions throughout their hospitalization. A full-recording study session will typically last approximately 8-12 hours (~8am-6pm or ~8pm-6am); some sessions may start earlier/later or go shorter/longer and in some instances we may study the subject for 24 hours (based on research personnel and equipment availability). The reasoning behind a shorter session and for having morning and evening start times is that as the subject matures, s/he may have 'wakeful' periods that prevent study in the crib/bed for certain periods throughout the day. The reasoning behind a 24-hr period is if we have available research-personnel support, we may study a subject throughout a complete 24-hr period to obtain diurnal responses. The number of full-recording sessions the subject participates will depend on duration of hospitalization (e.g., some subjects may be in the hospital longer than others, which will allow more opportunity to participate in multiple study sessions), on availability of research equipment and research personnel, and parent/guardian schedule (e.g., parent/guardian may prefer we not study the subject on certain days, for example if they want to spend time holding the subject or have visitors throughout the day). We will review the infant's/child's medical records and we will obtain additional history through questionnaire from the consenting parent/guardian. We will also obtain medical history on the subject's biological mother, including questionnaire and review of maternal medical records, if available through the UMass Memorial Healthcare system.

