Sessions will begin during the infant's/child's feeding, assessment or wake period, during which time sensors for the full-physiology/polysomnography recording will be applied by research study staff; sessions may begin any time if recordings are obtained directly from the bedside monitor. Periods of no intervention (NEATCap device OFF or SVS Mattress OFF) will be alternated with periods of intervention on (NEATCap device ON or SVS Mattress ON). The duration of each intervention period will conform to the routine care of the study subject. Because feeds vary as a function of subject's age, for example premature infants are typically on a fixed ~every 3-4 hours, whereas older infants and children may feed ad-libitum (i.e., as the child desires), the duration of intervention ON and OFF will vary within and between sessions and among subjects. The hospital standard of care for an individual subject, and the subject's sleep/wake cycle will determine the duration of the intervention periods. For subjects who may sleep throughout the night, periods of intervention will conform to either a routine assessment or medication interval (typically ~ every 3-4 hours) to allow for comparisons between intervention ON and intervention OFF with minimal disruption to the subject. The OFF-ON alternating cycles allow subjects to serve as their own control and ascertain if intervention ON leads to consistent, positive responses in the same subject, and assess whether the effect changes over the period.

NEATCap Intervention: At feed/assessment/wake period preceding a

NCT03881553 Study Protocol and Statistical Analysis Plan

NEATCap ON period, the NEATCap device will be fitted and placed on the child by research study staff. The NEATCap device will be removed (OFF) and replaced (ON) at alternating intervals throughout the study session. Physiological data will be recorded throughout the session while the subject is in the crib/bed or hospital-issued sleeping environment (e.g., motorized seat).

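### The Pearson correlation of IBI variance with movement duration names no unit of analysis; if periods are pooled and both measures cluster within child, its P value is too small

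*Combined protocol and SAP*

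**What the plan says.** Section 6, Statistical Procedures and Power Analysis, states that "Pearson product-moment correlation coefficient analysis will be used to establish associations between breathing stability (IBI variance) and movement duration". A positive correlation is expected, and P "values of <0.05 will be considered significant". The text attaches no unit to this correlation (child, session, period or shorter epoch) and does not say whether ON and OFF data are combined.

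The same section names repeated-measures handling for a different purpose: "separate repeated measures ANOVAs will test effects of stimulus condition (ON or OFF) and trial order". Nothing extends it to the correlation.

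The design makes the data repeated and unbalanced. Section 4, Study Sessions, lets a child "participate in up to 4 full-recording study sessions throughout their hospitalization". For children who may sleep through the night, "periods of intervention will conform to either a routine assessment or medication interval (typically ~ every 3-4 hours"). It adds that "the duration of intervention ON and OFF will vary within and between sessions and among subjects", and section 6 confirms that "The number of periods and duration of intervention will not always be the same for each study session".

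On movement, section 6 lists how often and how long body movements occur as separate quantities, with video, pulse-oximeter artefact and actigraph counts as example sources. It plans to explore "different durations of movement periods (e.g., 1.5-5 sec; >5 sec; >10sec").

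**The concern.** Two analysts could follow this text and run different tests of different questions. One value per child asks whether more restless children breathe less regularly. Pooled periods mix that with whether a given child breathes less regularly when moving more.

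The choice also affects the P value. A plain Pearson test treats every point as independent. Several periods from one child are not independent if that child tends to be high or low on both measures, so the pooled test would act as if it had more information than it has. A significant result could then appear too often when there is no association, and a reader could not tell which association it described.

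**Working it through.** **Inputs from the documents.** The threshold is 0.05 (section 6; two-sided assumed). Sessions typically last 8-12 hours, sometimes 24, with up to four per child, and periods last about 3-4 hours (section 4). **Assumptions.** The documents give no intraclass correlations (ICCs), periods per child or number of children for this analysis. The values below are therefore illustrative, and the simulations in steps 2, 4 and 5 use 40 children unless stated. Apart from the threshold there is no figure in the plan to reproduce.

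**Step 1: periods per child.** One session gives 8/4 = 2 to 12/3 = 4 periods, and four such sessions give 8 to 16. Three periods is about one session. Twelve needs three sessions at 4 periods, four at 3, or two 24-hour sessions at 24/4 = 6. Four sessions at 2 periods give only 8.

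**Step 2: pooled Pearson, no true association.** With m periods per child, the variance of r is inflated by about D = 1 + (m - 1) x ICC_x x ICC_y. The true type I error is 2 x (1 - Φ(1.96/√D)). With D = 1 this returns 5.0%. For m = 12 and both ICCs 0.5, D = 1 + 11 x 0.25 = 3.75, 1.96/√3.75 = 1.012, and the error is 31.1%. For unequal counts (10 children each with 2, 3, 6 and 12 periods), m is replaced by Σm²/Σm = 193/23 = 8.39.

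| Periods per child | ICCs 0.5/0 | 0.5/0.1 | 0.5/0.3 | 0.5/0.5 |
|---|---|---|---|---|
| 3: D | 1.00 | 1.10 | 1.30 | 1.50 |
| 3: formula | 5.0% | 6.2% | 8.6% | 11.0% |
| 3: simulated | 5.0% | 6.0% | 9.1% | 10.5% |
| 12: D | 1.00 | 1.55 | 2.65 | 3.75 |
| 12: formula | 5.0% | 11.5% | 22.9% | 31.1% |
| 12: simulated | 5.2% | 11.6% | 22.9% | 30.0% |
| Unequal: D | 1.00 | 1.37 | 2.11 | 2.85 |
| Unequal: formula | 5.0% | 9.4% | 17.7% | 24.5% |
| Unequal: simulated | 5.2% | 8.1% | 16.7% | 25.4% |

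The simulations used 5,000 runs per cell.

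**Step 3: conditions.** The first column shows that clustering in only one measure leaves the error near 5%, but this needs equal variances. With both ICCs zero and half the children having twice the standard deviation in both measures, the pooled test rejects in about 9% of runs at 12 periods.

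**Step 4: one mean per child.** With equal period counts the simulated error was 4.4-5.5% (20 and 50 children). With the unequal counts above it was 4.9-5.8% for ICC pairs from 0.5/0 to 0.5/0.5, but 6.6% at 0.1/0.1 and 9.4% at 0/0.

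**Step 5: candidate replacements.**
- Within-child correlation in the step 2 runs: 4.5-5.7%.
- With added clustering by session (2 or 4 sessions of 3 periods): 6.2-11.6% if session is ignored, 4.7-5.8% if centred within session.
- If the device shifts both measures by 0.5 SD and there is no other association (2-4 periods per child): 24-33% without an ON/OFF term, about 5% with it.
- Mixed model with an uncentred predictor (both ICCs 0.5, between-child correlation 0.5, no within-child association): significant in 32-35% of runs with 3 periods and 17-18% with 12. Centred on the child mean: 6% and 4%.

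**The case against.** The strongest reply is that the plan never says periods will be pooled. A reader might infer that the planned P value is wrong; the documents do not support that. The error needs both pooling and clustering in both measures, and every ICC and period count above is assumed. The largest figures come from the 12-period row, which describes a child studied well beyond one typical session. All of this stands, so the point is an unspecified analysis with a possible error, not a demonstrated one.

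A reader might also infer that movement duration is undefined. That goes too far. Section 6 separates frequency from duration, gives measurement sources and classes movements by length, so bout length is the natural reading. What remains is that total movement time is not ruled out, and that an unscaled total would depend on a period length that varies by design.

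Nor is one value per child a complete answer. Its error can reach 9.4% when period counts are unequal and clustering is absent, similar to pooling 3 periods with strong clustering.

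Finally, one might suspect that movement disturbs the respiratory belts and so creates the correlation. The documents do not say this, and true irregular breathing during movement would look the same. No movement-free analysis is asked for here.

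The reply does not remove the gap: the design produces repeated data, the named method ignores repetition, and the text does not say which data enter it.

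**Conclusion.** The concern holds in conditional form. If periods are pooled and both measures cluster within child, a nominal 5% test has a true type I error of about 6-11% with 3 periods per child and 12-31% with 12, under assumed ICCs of 0.5/0.1 to 0.5/0.5 (simulated with 40 children). It stays at about 5% if one measure does not cluster and variances are equal. If one value per child is used, the test is roughly valid, less so when period counts are unequal and clustering is weak, but it discards the within-child information that the design collects.

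The severity is low. This is a side association, and it would be wrong to infer that the ON/OFF comparisons are affected, since those have their own repeated-measures analysis. It is a cheap improvement.

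**What to change.** State the unit of analysis and replace the plain Pearson test for the within-child question with one of these:

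- a within-child (repeated-measures) correlation, adjusted for ON/OFF condition, and centred within session when a child has more than one session; or
- an equivalent mixed model in which the predictor is split into its child (or session) mean and the deviation from that mean, with an ON/OFF term and random effects for child and for session within child.

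The ON/OFF term and the split predictor are both needed, as step 5 shows. Without the first, a device effect on both measures appears as an association. Without the second, a difference between children can be reported as a change within a child.

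Report the between-child association separately, from one mean per child. Where period counts differ, a heteroscedasticity-robust (HC3) standard error is an option; it gave 5.1-5.7% in the unequal-count simulations.

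Clarify that movement duration means bout length or, if total movement time is meant, scale it by period length.

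The cost is a few sentences in section 6 and modest extra analysis of data already being recorded. The downsides are wider error bars and, with centring within session, loss of information on changes between sessions.

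### Section 6 does not separate a main outcome from exploratory ones: about 8 outcomes per device fall under one unadjusted P<0.05 rule, so an ineffective device has an assumed 10–18% chance of a false favourable result and 19–34% of one in either direction

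*Combined protocol and SAP*

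**What the plan says.** Section 6 (Statistical Procedures and Power Analysis) sets out what each device is to be assessed on. It names breathing (IBI), cardiac rhythm (R-R), "frequency and duration of body movements (e.g., defined via streamlined video, artifact in pulse-oximeter plethysmographic activity, and actigraph count"), and then "blood oxygenation (e.g., durations<85%), skin temperature, and sleep states". For one device it also asks "whether NEATCap device reduces dangerous levels of environmental noise". The list is given by way of example, not as a closed set. Further on, section 6 says the study tests whether each mode changes the time between feeds, benefits autonomic function and helps sleep.

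On methods, "Parametric tests will be used for analyses of all continuous variables", and "separate repeated measures ANOVAs will test effects of stimulus condition (ON or OFF) and trial order on physiological variables", followed by pairwise t-tests of ON against OFF. A correlation analysis is also planned, with the expectation that "greater variance in respiratory parameters will be positively correlated with excessive movement". One passage is worded as exploratory: "We will explore, for example, whether different durations of movement periods" relate differently to withdrawal or prematurity.

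The only decision rule is that P "values of <0.05 will be considered significant". It is not limited to any subset of these analyses. The text available for review gives no primary outcome, no order of testing, no adjustment and no power calculation from which a main outcome could be inferred.

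**The concern.** The three questions in section 6 are broad, and autonomic function alone covers several of the listed variables with no composite defined. Under the rule as written, any one of about 8 outcomes reaching P<0.05 could be reported as support for a device. A reader of the results could not tell a planned main finding from a chance one. Movement adds to the difficulty, because three ways of measuring it are offered and none is chosen.

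**Working it through.** The available text states no family-wise error rate, sample size or power, so there is no figure of the plan's own to reproduce.

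**Inputs from section 6**
- Threshold: 0.05 for every test. Sidedness is not stated; two-sided is assumed because the tests look for differences.
- Outcomes per device: (1) IBI, (2) R-R, (3) movement frequency, (4) movement duration, (5) oxygenation, (6) skin temperature, (7) sleep states, (8) interfeed interval. That makes 8. It is 7 if the two movement outcomes are merged, and 9 for NEATCap if environmental noise is an outcome and not a mechanism.

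**Assumptions**
- One ON/OFF test per outcome, each holding its 5% level.
- The device has no effect on any outcome.
- A common correlation ρ between test statistics. The documents give none, so ρ = 0.3 to 0.9 is shown.

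**Formulas**
- Independent, either direction: 1 − 0.95^k. For k = 8: 1 − 0.95^8 = 0.337.
- Independent, favourable direction only: 1 − 0.975^k. For k = 8: 1 − 0.975^8 = 0.183.
- Equally correlated z-tests, with c = 1.960: 1 − ∫ φ(x) [Φ((c − √ρ·x)/√(1−ρ)) − Φ((−c − √ρ·x)/√(1−ρ))]^k dx, by numerical integration. For the favourable direction, the second Φ term is dropped.

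**Chance of at least one false positive, one ineffective device**

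| Tests | Independent | ρ = 0.3 | ρ = 0.5 | ρ = 0.7 | ρ = 0.9 |
|---|---|---|---|---|---|
| 7, either direction | 30.2% | 27.2% | 23.0% | 17.8% | 11.4% |
| 8, either direction | 33.7% | 30.0% | 25.0% | 19.1% | 11.9% |
| 9, either direction | 37.0% | 32.6% | 26.9% | 20.2% | 12.4% |
| 8, favourable only | 18.3% | 15.2% | 12.5% | 9.5% | 6.0% |

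For a single test the corresponding rates are 5% (either direction) and 2.5% (favourable).

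**Check with small samples.** Simulated paired t-tests, 8 outcomes, either direction, at assumed sample sizes of 50 down to 10, gave 30.3–30.9% at ρ = 0.3 and 19.4–20.8% at ρ = 0.7. The normal approximation is adequate.

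**Narrowest count.** If section 6 is read as only three tests (interfeed interval, autonomic function, sleep), the independent either-direction rate is 1 − 0.95^3 = 0.143, or 14%. Three is a lower bound on the count, because autonomic function has several components and no composite.

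**Not counted.** Trial-order and covariate effects, post-hoc t-tests, movement-duration bands, the Pearson correlation, alternative movement measures and the second device are all left out.

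**The case against.** Four points can be made for the plan.

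1. *A primary outcome may exist elsewhere.* Section 4 refers to a section 32 and section 6 to exclusion criteria, and neither is in the available text, which also has no objectives or endpoints section. If a primary is named there, the figures above are not the error rate of the main claim. What would remain is that section 6 gives that outcome no special role. This stands as a limit on the finding.

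2. *A false benefit claim needs an error in the right direction.* A reader might infer from 34% that an ineffective device has a one-in-three chance of being declared beneficial. The documents do not support that. Two of the three questions in section 6 are directional, and the 34% includes apparent harm and assumes independence. The favourable-direction figures are about half as large. The either-direction rate is still worth stating, since the favourable direction is not defined for every variable, skin temperature for example.

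3. *The count and the correlations are inferred.* The variables are introduced as examples, and no correlation between tests is given. The expected association between breathing variance and movement concerns raw measures and need not carry over to ON-OFF test statistics. This stands; it is why ranges are shown.

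4. *The study is largely exploratory.* Section 6 speaks of quantification and exploration, and section 5 expects no clinically important information in the short term. Strict family-wise control would be more than such a study needs. But section 6 also uses the language of testing, and its significance rule does not separate the two kinds of analysis.

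**Conclusion.** The concern holds in a limited form: section 6, as available, does not distinguish a main outcome from exploratory ones, and one unadjusted threshold covers about 8 outcomes per device. The rule followed as written raises the chance of a false favourable result from 2.5% for one test to about 18% if the 8 tests are independent, or 10–15% at correlations of 0.7–0.3. In either direction the rise is from 5% to 34%, or 19–30%. Even at a correlation of 0.9, the rates are 6% and 12%.

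These figures rest on an inferred count, assumed correlations, one ON/OFF test per outcome, and tests that hold their 5% level. The last is itself uncertain, because section 6 says the number and length of periods vary.

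A reader might also infer that the trial has no primary outcome, or that adjustment has been ruled out. Neither can be said. The absence is established only for the available text, and that text is silent on adjustment without excluding it.

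**What to change.** In section 6:

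- Name one primary outcome per device and one movement measure. Carry over any primary already named elsewhere in the protocol. Otherwise the investigators choose on scientific grounds, and the choice is dated and made without sight of ON/OFF results. That condition is needed because the Covid-19 procedures in section 4 show that enrolment and bedside studies had already begun before they were halted.
- State whether sessions using both devices, which section 4 allows, count toward either device's claim.
- Test the ON-OFF effect on the primary at 0.05 as the basis for that device's claim.
- Report every other outcome as secondary or exploratory, with estimates and confidence intervals, and make no device claim from a single P<0.05 among them.

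The cost is wording only, and the primary keeps its full 0.05, so it loses no power. The downside is that a significant secondary outcome can no longer support a device claim by itself. The remaining chance of a false positive on the primary is 5% per device. If neither device works, it is up to about 10% across both (1 − 0.95^2 = 0.0975). Both figures require that the chosen test holds its level when periods are unequal.
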